#### 4.8. Sub-Populations

## 4.8.1. Urinary Antigen Detection (UAD) Subpopulation

The UAD subpopulation will include all participants in the per-protocol population that have at least one valid UAD result, i.e., the participants should have UAD results as 'POS' or 'NEG' for any of the 24 serotypes. For each serotype, there are 5 possible values:

- "POS" Positive
- "NEG" Negative
- "INDETERMINATE"
- 4. "QNS" quantity not sufficient
- "NOT DONE" urine was received by VRED laboratory but the test was not done on the sample

The UAD subpopulation will exclude the participants that have

- "INDETERMINATE" results for all 24 serotypes, or
- QNS results for all 24 serotypes, or
- NOT DONE results for all 24 serotypes, or
- had any combination of QNS/ indeterminate/NOT DONE results for all 24 serotypes

#### 4.8.2. Binax Subpopulation

The Binax subpopulation will include all participants from the per-protocol population that have valid Binax results ('POS' or 'NEG'). There will only be one result per urine sample test. There are four possible values:

- "POS" Positive
- "NEG" Negative
- "QNS" quantity not sufficient
- "NOT DONE" urine was received by VRED laboratory but the test was not run on the sample.

The Binax subpopulation will exclude the participants that have QNS results, or NOT DONE

## 4.8.3. Microbiology Culture Subpopulation

The microbiology culture subpopulation will include all participants that are included in the perprotocol population and have non-missing culture results (i.e., 'No Growth', 'Streptococcus Pneumoniae' or growth attributable to another pathogen).

DMB02-GSOP-RF02 5.0 Statistical Analysis Plan Template 05-Dec-2019
PFIZER CONFIDENTIAL
Page 26
TMF Doc ID: 98.03

#### 4.8.4. Viral Pathogen Testing Subpopulation

The viral testing subpopulation will include all participants that are included in the per-protocol population and have non-missing viral pathogen testing results (i.e., 'Not done').

## 4.8.5. Sp+ Subpopulation

This subpopulation is composed of the per-protocol population that are also Sp+ by any of the following three diagnostic methods:

- microbiology culture results of S. pneumoniae as a pathogen from local lab entered in the eCRF; or
- 'POS' results from Binax assay; or
- 'POS' results from UAD assay for any of the 24 serotypes.

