#### 3.2. Secondary Endpoint(s)

 Proportion of CAP events for each pneumococcal serotype, PCV-13, and 20-valent pneumococcal conjugate vaccine (PCV20) serotypes among all CAP subjects with UAD1/2 testing (overall) and among all CAP subjects with a pneumococcus identified.

The denominators for this endpoint are:

- all CAP patients having their UAD 1 or 2 results available,
- all CAP patients with a pneumococcus identified (Sp+) from UAD, Binax, blood culture, or high-quality respiratory cultures

Note: If a participant, for example, is positive for a PCV20 serotype (e.g., 8) and a non-PCV20 serotype (e.g., 17F), the participant will be counted as PCV20 Sp+ and not non-PCV20 Sp+.

 Proportion of CAP events where the pneumococcus was identified from saliva by culture or PCR divided by all CAP events where the subject had a valid saliva specimen test result.

DMB02-GSOP-RF02 5.0 Statistical Analysis Plan Template 05-Dec-2019
PFIZER CONFIDENTIAL
Page 10
TMF Doc ID: 98.03

The denominator will be the CAP population with valid saliva specimen test result.

- Proportion of CAP subjects with underlying at-risk and high-risk medical conditions, overall and restricted to those with pneumococcus isolated from blood, high-quality respiratory cultures, and a serotype-specific urinary antigen detection (UAD) assay.
  - For overall, the denominator will be all CAP population. For participants restricted to pneumococcus, the denominator will be the CAP population in whom a pneumococcus is identified from culture, UAD, or Binax.
- Proportion of S. pneumoniae isolates with antibiotic resistance identified by standard of care testing, overall and by resistance type.

The analysis will be conducted among participants who are Sp+ by culture among the CAP population for whom the data on antibiotic resistance are available. If the antibiotic resistance information is missing or not done for a participant, then the participant will be excluded from the analysis. For participants whose Sp isolates were shipped to the Reference Lab, antibiotic resistance results will be used in the analysis. Participants who are detected as Sp+ via culture method but without serotype information ('Not Serotyped') will also be included in the analysis.

Antibiotic resistance will be reported in the eCRF as one of the following categories:

- SUSCEPTIBLE
- RESISTANT
- NOT APPLICABLE
- o UNKNOWN

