#### Results of Culture and Urine Assays for S. pneumoniae

Sp+ is defined as the identification of Streptococcus pneumoniae via any of the following three diagnostic methods:

Microbiology culture: As part of standard of care, all blood and respiratory specimens (e.g., blood, pleural fluid, transtracheal aspirate, bronchoalveolar lavage or other respiratory tract specimen) will undergo bacterial culture at the local site laboratory for the identification of S. pneumoniae according to their standard methodology. Results of blood cultures (including antibiotic susceptibility) from this standard of care bacterial culture testing will be recorded in the CRF.

DMB02-GSOP-RF02 5.0 Statistical Analysis Plan Template 05-Dec-2019
PFIZER CONFIDENTIAL
Page 21
TMF Doc ID: 98.03

For sputum specimens collected as part of SOC testing, specimen quality will be assessed using the specimen's standard-of-care Gram stain results. Only bacterial culture results from high-quality sputum specimens will be used in case of categorization for the VE analysis. However, all pneumococcal isolates will be serotyped regardless of specimen quality.

Pneumococcal bacterial isolates from standard of care specimens will be shipped and analyzed in the Pneumococcal Reference Laboratory from the Centro Nacional de Microbiología of the Instituto de Salud Carlos III (ISCIII). The following antimicrobials will be evaluated: penicillin, amoxicillin, cefotaxime, erythromycin, clindamycin, tetracycline, and levofloxacin.

- Binax assay: If a positive result is issued from the urine testing, when analysed by the Pfizer VRD laboratory, then it is considered Sp+. This assay does not provide Sp serotype information.
- UAD assay: The UAD-1 detects 13 serotypes (1, 3, 4, 5, 6A, 6B, 7F, 9V, 14, 18C, 19A, 19F, 23F) used in Pfizer's 13vPnC vaccine. The UAD-2 assay, using the same Luminex xMAP bead technology, detects 11 additional serotypes (2, 8, 9N, 10A, 11A, 12F, 15B, 17F, 20, 22F, 33F). A maximum of two serotypes can be reported from each one of the UADs.

Any participant who is not determined as Sp+ by any of the three diagnostic methods will be considered as Sp-, unless they have missing results from all three diagnostic methods. If any culture identified Sp+, antibiotic susceptibility will be assessed at the local laboratory and results are to be entered in the CRF.

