## 4.3. Per-Protocol Population

The per-protocol population consists of all participants in the all enrolled population who met all inclusion/exclusion criteria. Any participant who is included in the 'all enrolled population' will be excluded from per-protocol population if the participant did not meet the inclusion/exclusion criteria. A participant with an important protocol deviation as ascertained by the clinical team will also be excluded from the per-protocol population.

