#### 4.5. The CAP Population

The CAP population will include the per-protocol population and who have a final diagnosis consistent with CAP (CAP-radiologically confirmed; CAP not radiologically confirmed, or CAP-no chest radiology done).

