#### 6.2.3.1. Secondary Endpoint 3 - Main Analysis

The following calculations will be made, overall and by risk condition:

- Proportion of participants (with 95% CI for proportion) with at-risk medical condition among all CAP population
- Proportion of participants (with 95% CI for proportion) with high-risk medical condition among all CAP population

DMB02-GSOP-RF02 5.0 Statistical Analysis Plan Template 05-Dec-2019
PFIZER CONFIDENTIAL
Page 35
TMF Doc ID: 98.03

- Proportion of participants (with 95% CI for proportion) with at-risk medical condition among the Sp+ subpopulation
- Proportion of participants (with 95% CI for proportion) with high-risk medical condition among the Sp+ subpopulation

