# 6.3.5.1. COVID-19 Related Endpoint 1 - Main Analysis

The following calculations will be made for overall and stratified by age group, sex, and pneumococcal risk status among COVID-19 subpopulations (test positive or negative), i.e., all enrolled population with a valid results from COVID-19 viral testing. The following calculations will be made:

- Proportion (95% CI for proportion) of CAP events with pneumococcus among COVID-19 test positive cases
- Proportion (95% CI for proportion) of CAP events with pneumococcus among COVID-19 test negative cases

These will also be calculated for the following subgroups: age group (60-74 years, 75-84 years and ≥85 years), sex, and pneumococcal risk status.

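### The SAP's Sp+ subpopulation requires neither a final CAP diagnosis nor a high-quality culture, so it does not match the secondary endpoints that use it; COVID-19 endpoint 1 has a similar mismatch of base population.

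*SAP*

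**What the plan says.** SAP 4.8.5 opens: "This subpopulation is composed of the per-protocol population that are also Sp+ by any of the following three diagnostic methods". The culture limb is "microbiology culture results of S. pneumoniae as a pathogen from local lab entered in the eCRF; or", and the other two limbs are a positive Binax and a positive UAD for any of the 24 serotypes. On the base set, SAP 4.3 states: "The per-protocol population consists of all participants in the all enrolled population who met all inclusion/exclusion criteria". It also removes important protocol deviations, but final diagnosis is not a condition. The CAP population of SAP 4.5 is narrower: "The CAP population will include the per-protocol population and who have a final diagnosis consistent with CAP".

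The endpoints are worded differently. For secondary endpoint 1 (serotype distribution), one of the two denominators in SAP 3.2 is "all CAP patients with a pneumococcus identified (Sp+) from UAD, Binax, blood culture, or high-quality respiratory cultures". Secondary endpoint 3 (risk conditions) is defined in protocol section 8 and SAP 3.2 among CAP subjects, restricted to pneumococcus from blood, high-quality respiratory culture or UAD. SAP 6.2.3 adds Binax. The calculation in SAP 6.2.3.1 is then the proportion "with at-risk medical condition among the Sp+ subpopulation", with a parallel line for high-risk conditions.

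COVID-19 endpoint 1 is a percentage of CAP events (SAP 3.3.2 and 6.3.5). SAP 6.3.5.1 runs it on "all enrolled population with a valid results from COVID-19 viral testing", while SAP 4.8.8 defines the COVID-19 subpopulation as per-protocol.

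**The concern.** Final diagnosis is settled at Visit 2 (protocol 10.4) and may be acute bronchitis, exacerbation of COPD, exacerbation of heart failure or a non-infectious process. Protocol exclusion criterion 6 removes only patients whose pneumonia has been ruled out by enrolment, so some per-protocol patients can end as non-CAP. If they are Sp+ under SAP 4.8.5, they enter the denominators of SAP 6.2.3.1.

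For secondary endpoint 3 this contamination need not be neutral. COPD and congestive heart failure are themselves at-risk conditions in SAP Appendix 2.4, so a patient whose final diagnosis is an exacerbation of either will normally count as at-risk or high-risk.

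On the culture side, an isolate from poor-quality sputum may reflect carriage rather than infection. That is why the endpoint texts ask for high-quality specimens.

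Two programmers following different sections of the same SAP could therefore deliver different secondary results.

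**Working it through.** **Step 1: the definitions side by side.** No stated figure has to be reproduced, because the documents give no Sp+ rate.

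| Place | Base | Culture | Binax |
|---|---|---|---|
| SAP 3.2, endpoint 1 denominator | CAP | blood or high-quality respiratory | yes |
| SAP 6.2.1.1 (endpoint 1) | CAP | no quality limit | yes |
| Protocol section 8, endpoint 3 | CAP | blood or high-quality respiratory | not named |
| SAP 3.2, endpoint 3 text | CAP | blood or high-quality respiratory | not named |
| SAP 3.2, endpoint 3 denominator note | CAP | no quality limit | yes |
| SAP 6.2.3 | CAP (heading) | blood or high-quality respiratory | yes |
| SAP 6.2.3.1, through 4.8.5 | per-protocol | any local culture recorded as a pathogen | yes |

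UAD counts in every row. Only the last row lacks the CAP restriction. Three rows lack the quality limit. The Sp+ RAD+CAP subpopulation (SAP 4.8.6) has the same culture limb, but its base is already CAP.

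**Step 2: COVID-19 endpoint 1.** The CAP population lies inside the per-protocol population, which lies inside all enrolled. The endpoint counts CAP events, SAP 4.8.8 uses the middle set, and SAP 3.3.2 and 6.3.5.1 use the widest. One endpoint thus has three candidate bases.

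**Step 3: illustrative size.** All inputs here are assumptions.

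(a) Non-CAP share of the Sp+ set. Let f be the non-CAP share of per-protocol patients (2% to 15%), p the Sp+ rate in CAP (15% to 30%) and q the Sp+ rate in non-CAP (5% to 15%). Then s = fq / [fq + (1 − f)p].
- Lowest: 0.02 × 0.05 / (0.02 × 0.05 + 0.98 × 0.30) = 0.001 / 0.295 = 0.3%.
- Intermediate: 0.10 × 0.10 / (0.10 × 0.10 + 0.90 × 0.15) = 0.010 / 0.145 = 6.9%.
- Highest: 0.15 × 0.15 / (0.15 × 0.15 + 0.85 × 0.15) = 0.0225 / 0.150 = 15%.

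(b) Shift in a risk-condition proportion. Let d be the difference in prevalence between non-CAP and CAP patients (10 to 20 points). The shift is s × d.
- s = 1%, d = 10: 0.1 points.
- s = 10%, d = 20: 2.0 points.
- At the extremes of (a): 0.0034 × 10 = 0.03 points and 0.15 × 20 = 3.0 points.

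(c) Low-quality sputum. Let m be the share of CAP patients positive only on low-quality sputum (0.5% to 2%). The relative rise in the Sp+ count is m / p.
- Lowest: 0.005 / 0.30 = 1.7%.
- Highest: 0.02 / 0.15 = 13.3%.

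**The case against.** The best defence is that the per-protocol base is deliberate. SAP 6.5.2 breaks the per-protocol population down by Sp+ and Sp−, and SAP 6.5.5 asks for the same split within CAP and within non-CAP. Redefining Sp+ itself as CAP-only would leave the non-CAP Sp+ cell of 6.5.5 empty. This stands, and it shapes the fix.

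The CAP restriction is also stated in SAP 3.2, in 6.2.1.1 and in the heading of 6.2.3, so the fault is an internal contradiction rather than a settled rule. That stands too, but the bullets of 6.2.3.1 name the wider set. Recording an isolate as a pathogen softens the culture limb, yet it is not the Appendix 4 criterion.

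A reader might infer more than the documents support:

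- **The sputum-quality rule is confined to vaccine effectiveness.** It is not. It also appears in SAP 3.2, 4.7, 6.2.1 and 6.2.3.
- **Sp+CAP incidence is inflated.** No section ties it to SAP 4.8.5, and protocol 12.4.2 uses CAP events with pneumococcus identified by any means.
- **Standard-of-care urine antigen is wrongly omitted.** The secondary endpoints do not list it, and protocol 9.1 plans central Binax and UAD for all enrolled participants.
- **The Suzuki controls are misdefined.** Their list of methods (culture, UAD, Binax) is the protocol's own, in 12.1.1.
- **The primary result is at risk.** SAP 3.1 requires a final CAP diagnosis for cases and a high-quality specimen for any sputum isolate that assigns case status.

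**Conclusion.** The mismatch is real and limited to descriptive secondary and exploratory outputs. Secondary endpoint 3 is the most exposed, because SAP 6.2.3.1 applies the unrestricted set. Secondary endpoint 1 is exposed on specimen quality only. COVID-19 endpoint 1 has a base that does not match its definition.

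The size cannot be derived from the documents. On the assumed ranges, 0.3% to 15% of the Sp+ set is non-CAP. The risk proportions shift by about 0.1 to 2 percentage points when 1% to 10% of the set is non-CAP. Low-quality sputum raises the Sp+ count by about 2% to 13%. Primary vaccine effectiveness is unaffected.

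**What to change.** 1. Keep the per-protocol Sp+ flag of SAP 4.8.5 for the summaries in 6.5.2 and 6.5.5.
2. Add an Sp+CAP set to SAP section 4: CAP population, and S. pneumoniae from blood, pleural fluid or an Appendix 4 high-quality respiratory culture, or a positive UAD-1/2, or a positive Binax.
3. Use that set in SAP 6.2.1.1 and 6.2.3.1, and align the plain reference to culture in the endpoint 3 denominator note of SAP 3.2.
4. For secondary endpoint 3, also show the protocol version without Binax.
5. Base SAP 6.3.5.1, and the matching sentence in 3.3.2, on CAP-population patients with a valid COVID-19 result. That endpoint keeps its identification of pneumococcus by any means.

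The cost is SAP wording, one derived flag and one extra display. Final diagnosis, specimen type and Gram stain results are already collected.

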## 4.8.6. Sp+ RAD+CAP Subpopulation

This subpopulation is composed of participants in the RAD+CAP population that are also Sp+ by any of the following three diagnostic methods:

- microbiology culture results of S. pneumoniae as a pathogen from local lab entered in the eCRF; or
- 'POS' results from BinaxNOW assay; or
- 'POS' results from UAD assay for any of the 24 serotypes.

#### 4.8.7. Sp- RAD+CAP Subpopulation

This subpopulation is composed of the participants in the RAD+CAP population who are not included in the Sp+ RAD+CAP subpopulation.

#### 4.8.8. COVID-19 Subpopulation

This subpopulation will include participants in the per-protocol population with a valid result from COVID-19 viral pathogen testing.

#### 4.8.9. COVID-19 Postive Subpopulation

This subpopulation will include participants in the per-protocol population and who are positive for COVID-19 from a valid result from COVID-19 viral pathogen testing.

## 4.8.10. COVID-19 Negative Subpopulation

This subpopulation will include participants in the per-protocol population and who are negative for COVID-19 from a valid result from COVID-19 viral pathogen testing.

#### 4.8.11. Pneumococcal Carriage Subpopulation

This subpopulation will include the per-protocol population for whom a valid penumoccocal carriage result is available from saliva samples.

## 4.8.12. RSV Subpopulation

This subpopulation will include the per-protocol population for whom a valid RSV result is available either from the study testing or SOC.

#### 4.8.13. RSV Positive Subpopulation

This subpopulation will include the per-protocol population with a positive RSV result either from the study testing or SOC.

#### 4.8.14. RSV Negative Subpopulation

This subpopulation will include the per-protocol population with a negative RSV result either from the study testing or SOC.

#### 5. GENERAL METHODOLOGY AND CONVENTIONS

#### 5.1. Hypotheses and Decision Rules

The decision rule determines under what circumstance to reject the null hypotheses. There is no hypothesis test and no decision rule applied in this study. The objective of this study is to evaluate the PCV13 VE against hospitalised VT-CAP among adults aged ≥60 years.

## 5.2. General Methods

#### 5.2.1. Analyses for Binary Endpoints

Binary data will be summarized with counts and percentages. For the purpose of comparing two binary variables, 2×2 contingency tables will be used with cell frequencies and percentages. Percentages will be based on of the total number of participants used in the analysis (i.e., participants with both binary variables recorded). The number and percent of concordant and discordant results will also be calculated. Some of the endpoints may be summarized with exact 95% confidence intervals (CIs) for the proportion of interest. The exact 95% CI will be calculated based on the Clopper-Pearson method (Appendix 3.1)

#### 5.2.2. Analyses for Categorical Endpoints

Categorical data will be summarized as the number of participants, as well as number of isolates, included in the analysis, frequencies and percentages of the individual categories. Pneumonia

DMB02-GSOP-RF02 5.0 Statistical Analysis Plan Template 05-Dec-2019
PFIZER CONFIDENTIAL
Page 28
TMF Doc ID: 98.03

severity will be categorized as grade I (PSI Score=0), II (PSI Score=1-70), III (PSI Score=71-90), IV (PSI Score=91-130), and V (PSI Score>130) and analyzed also as the categorical variable. All percentages will be based on the total number of participants or isolates included in the analysis.

## 5.2.3. Analyses for Continuous Endpoints

Continuous variables will be summarized as the number of participants included in the analysis, mean, standard deviation, median and range. The applicable variables will include demographics, e.g., age at enrollment, weight, height, BMI, duration of ICU stay, duration on ventilator, duration of hospital stay, and PSI score. Participants with a missing value will be excluded from the analysis for that variable.

## 5.2.4. Analysis of Incidence Rates

An incidence rate is defined as the proportion of new disease cases out of the total number of individuals at risk of developing that disease over a specified period of time. The numerator will be the number of disease cases (CAP events captured from eCRF and Screening Log) residing in the hospitals' catchment area and the denominator will be the total number of individuals living in the hospitals' catchment area. No adjustment will be made, such as market share, to adjust the population because the hospitals serve a defined population based on the structure of health service delivery in this region. This data on the denominator will come from government data sources (e.g., census) or other population data sources. Note that the start of the incidence surveillance period will be when surveillance is considered complete at both study sites, i.e, when it is confirmed that all pneumonia events are being captured on the screening log.

The incidence rate will be calculated per 100,000 population per year in each specific age groups (60-74 years, 75-84 years and ≥85 years) as well as all ages of the study. The formula for calculating the incidence rate is given and the analysis section, and 95% CIs for the incidence rate will be based on the assumption that the actual count of cases arises from a Poisson distribution. Further details of the approach to CIs calculations are given in Appendix 3.2.

## 5.3. Methods to Manage Missing Data

Analyses will be based on all available data. Participants who have data missing for a certain analysis will be excluded only from that analysis. For example, if a participants has missing UAD assay results but has results available from Binax and culture, then the participants will be excluded from any analyses requiring the UAD results, but will be included in any analyses requiring results from Binax or culture.

#### 5.4. Serotype Determination

A subject may have 2 different serotypes identified from UAD-1. Similarly, the participants may have 2 different serotypes identified from UAD-2, totaling a maximum of 4 different serotypes from UADs. Participants can also have multiple Sp isolates from microbiology cultures. All Sp isolates are sent to the Reference Lab for serotyping. If multiple Sp isolates are serotyped and found to be the same serotype they will be counted one in the serotype distribution. If multiple isolates are sent to the Reference Lab and have different serotypes, they will be counted once for

DMB02-GSOP-RF02 5.0 Statistical Analysis Plan Template 05-Dec-2019
PFIZER CONFIDENTIAL
Page 29
TMF Doc ID: 98.03

each unique serotype. However, if no Sp isolates were serotyped, then 'not serotyped' will be considered in the serotype distribution.

Subjects may also be identified with 4 or more different isolates/serotypes from the two diagnostic methods (culture and UADs). For subjects who are Sp+ via culture method but without serotype information ('Not Serotyped'), the following approaches are used:

- a. If subjects had multiple isolates identified as Sp+ from culture which are 'Not Serotyped', those will be counted as only one in the numerator when summarizing 'Not Serotyped' in the analysis of 'percent of isolates'
- If subjects are identified as Sp+ from UAD, serotypes from UAD will be included in the numerator of the numbered serotype(s).
- c. If subjects were NOT identified as Sp+ from UAD, the subjects with isolates not serotyped will be included in the numerator when summarizing 'Not Serotyped' and 'Any Sp+' in the analysis of 'percent of subjects'. The isolates will also be included in the numerator of 'Not Serotyped' for the analysis of 'Percent of Isolates'. However, only one "Not serotyped" isolate will be counted in the numerator.

For subjects who are detected as Sp+ via culture and UAD, the following approaches are used:

- a. If the same serotype is identified, the serotype will only be counted once in the analysis of 'percent of serotypes'.
- If different serotypes are identified, all unique serotypes from both methods will be in analysis of 'percent of serotypes

